To form a reasonable basis of safety for enrolling the expansion cohort of patients, this study will incorporate two safety lead-ins using the first 6 patients and the first 15 patients (50% of the expected total number of patients) to assess the feasibility, safety and tolerability of combining TTFields therapy with concurrent chemoradiation (concurrent enrollment allowed). The safety cohorts will receive TTFields therapy in addition to standard of care. Variations in daily patient positioning will be recorded. Any treatment related adverse effects will be measured, assessed, and graded during the dose-limiting toxicities (DLT) period, from the beginning of therapy until 8 weeks after completion of radiation therapy to capture any potential delayed toxicity following combination (Trimodal) therapy with radiation, temozolomide, and TTFields therapy. DLT include any severe or life-threatening treatment-related adverse effects that preclude further administration of the study treatments, such as radiation, temozolomide, or continuation of TTFields therapy. The DLT assessment period will be limited to the time from start of TTFields through 8 weeks after RT's completion.

The first lead-in cohort will include the first 6 patients to finish the DLT period and be assessed by investigators. If a DLT occurs in 2 or more of the 6 patients, then the study will not move forward and may re-consider the goal dose of TTFields therapy in the main cohort to be reduced by 50% (one out of every two weeks off) and only increased to the standard usage of

continuous treatment 4 weeks after completion of radiation therapy. If a DLT occurs in less than two patients, the study will proceed with the second safety lead-in.

The second lead-in cohort will include the first 15 patients (6 from the first lead-in and 9 additional) to finish the DLT period and be assessed by the Data Safety Monitoring Committee (DSMC). If a DLT occurs in 5 or more of the 15 patients in the second safety cohort, then the study will not move forward with the expansion cohort and may re-consider the goal dose of TTFields therapy in the main cohort to be reduced by 50% (one out of every two weeks off) and only increased to the standard usage of continuous treatment 4 weeks after completion of radiation therapy. If a DLT occurs in less than five patients, the study will proceed with the final expansion cohort.

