7. SUBJECT ASSESSMENTS FOR SAFETY AND EFFICACY

The study procedure calendar for this study is provided in **Appendix 3**.

a) Evaluation of Safety and Tolerability**Dose Limiting Toxicity**

Dose limiting toxicities (DLTs) are defined as any severe or life-threatening treatment-related toxicity that precludes the use of a specified dose of any of the study treatments (TTFields, temozolomide, radiation) including continued use of Optune TTFields device at the standard treatment levels and schedule set out by prior studies. This study will prioritize preserving the standard of care for glioblastoma using approved dosing and radiation of temozolomide and radiation.

Toxicities will be graded according to the CTCAE (Version 5.0) scale. If multiple toxicities are seen, the presence of DLT should be based on the most severe toxicity experienced. Dose-limiting toxicities will be defined as any of the following events which occur during the experimental trimodal therapy with TTFields is added concurrently to radiation and temozolomide therapy or during the 8 weeks after RT is completed, and are considered by the investigator to be attributable to TTFields or the combination of TTFields with radiation and/or temozolomide:

- Any Grade > 3 thrombocytopenia, and Grade 4 anemia and neutropenia.
- Any nonhematologic Grade > 3 toxicity (including nausea, vomiting, or diarrhea), excluding alopecia.

- Any Grade 3-4 radiation-induced skin changes that persist for greater than 7 days and does not improve with management recommendations as outlined in toxicity management.
- Any adverse effect deemed by the investigator, patient's primary neuro-oncologist, or radiation oncologist to be life threatening in nature.

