In the event of a dose-limiting toxicity, the subject will be discontinued from treatment and followed for toxicity assessment and management and a joint decision will be made by the investigator and sponsor whether to adjust the dose or schedule for other subjects or permanently close the study for safety. In the event that more than 33% of subjects experience a DLT, the study cannot continue unless a modification is made to the level of the particular treatment to which that adverse event is definitely attributable. As preliminary safety stops, the study will include two safety lead-ins receiving TTFields with concurrent chemoradiation. These initial 6 and then 15 subjects will undergo interim analyses after completion of chemoradiation to determine if the expanded cohorts should be permitted enrollment as planned or if a dose reduction in TTFields of 50% of the scheduled use is warranted for safety.

Subjects will continue to receive study treatment until confirmed tumor progression, unacceptable toxicity, or other discontinuation criteria as described; subjects MUST discontinue investigational product (and non-investigational product at the discretion of the investigator) if they meet criteria for removal from study therapy as referenced in that section.

Toxicity related to TTFields treatment: Treatment-related adverse events (TRAEs) and severe treatment-related adverse events (STRAEs) will be assessed in the following ways.

- Patients will be evaluated by a neuro-oncologist or radiation oncologist for potential skin toxicity from TTFields therapy. Routine skin care recommendations will be provided, including use clobetasol cream prior to electrode placement and adjusting array placement to avoid continued site irritation. If there are concerns by investigator, the subject will be referred to a dermatologist for specialized evaluation. Neurological and general physical evaluations as well as laboratory assessments will also be conducted by a neuro-oncologist or radiation oncologist to identify other potential toxicities.
- In addition to clinic visits and interventions, Patients will also be supported by a technician from Novocure for device troubleshooting and compliance checks.
- All other adverse effects, either mild, or serious, will be triaged by a physician in coordination with the primary investigators of the study.

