prevent one of the outcomes listed in this definition. Examples of such medical events include allergic bronchospasm requiring intensive treatment in an emergency room or at home, blood dyscrasias or convulsions that do not result in inpatient hospitalization, or the development of drug dependency or drug abuse.

Life-threatening

An adverse event or suspected adverse reaction is considered *life-threatening* if, in the view of either the investigator or sponsor, its occurrence places the patient or subject at immediate risk of death. It does not include an adverse event or suspected adverse reaction that, had it occurred in a more severe form, might have caused death.

Recording of an Adverse Event

All grade 3 and above adverse events will be entered into the CTMS, Velos, whether or not the event is believed to be associated with use of the study device. Data about these events and their severity will be recorded using the NCI CTCAE v5.0.

All SAEs will be reviewed by a DSMC, which will consist of a panel of experts in oncology, neuro-oncology, biostatistics, or radiation oncology who are not direct investigators in this study. The PI will identify members of the DSMC and receive feedback and recommendations from the DSMC as to the safety of continuing the trial. The PI and study manager will be responsible for facilitating the proceedings as non-committee members. The committee will meet twice a year, or more if needed.

The Investigator will assess all adverse events, assign attribution of the possible association of the event with use of the investigational device, and this information will be entered into CTMS (Velos) using the classification system listed below:

Relationship	Attribution	Description
Unrelated to investigational drug/intervention	Unrelated	The AE is clearly NOT related to the intervention
	Unlikely	The AE is doubtfully related to the intervention
Related to investigational drug/intervention	Possible	The AE may be related to the intervention
	Probable	The AE is likely related to the intervention
	Definite	The AE is clearly related to the intervention

A more detailed definition of possible attributions is denoted in the following table:

Unrelated:	The event is clearly related to an event that may be due to environmental or accidental occurrence or other factors such as the subject's clinical state, therapeutic interventions, or concomitant drugs administered to the subject.
------------	--

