Unlikely	The event is most likely produced by other factors such as the subject's clinical condition, therapeutic interventions, or concomitant drugs administered to the subject, and does not follow a known response pattern to the study drug or device.
Possible	The event follows a reasonable temporal sequence from the time of drug administration or use of device, and/or follows a known response pattern to the study drug or device, but could have been produced by other factors such as the subject's clinical condition, therapeutic interventions, or concomitant drugs administered to the subject.
Probable	The event follows a reasonable temporal sequence from the time of drug administration or use of device, and follows a known response pattern to the study drug or device, and cannot be reasonably explained by other factors such as the subject's clinical condition, therapeutic interventions, or concomitant drugs administered to the subject.
Definite	The event follows a reasonable temporal sequence from the time of drug administration or use of device, and follows a known response pattern to the study drug or device, and cannot be reasonably explained by other factors such as the subject's clinical condition, therapeutic interventions, or concomitant drugs administered to the subject, and either occurs immediately following study drug administration or use of device or improves on stopping the study drug or device, or reappears on repeat exposure

The relationship of the adverse event to the study treatment must be specified using the following definitions:

Signs or symptoms reported as adverse events will be graded and recorded by the Investigator according to the CTCAE. When specific adverse events are not listed in the CTCAE they will be graded by the Investigator as *none*, *mild*, *moderate* or *severe* according to the following grades and definitions:

- Grade 0 No AE (or within normal limits)
- Grade 1 Mild; asymptomatic or mild symptoms; clinical or diagnostic observations only; intervention not indicated
- Grade 2 Moderate; minimal, local, or noninvasive intervention (e.g., packing, cautery) indicated; limiting age-appropriate instrumental activities of daily living (ADL)
- Grade 3: Severe or medically significant but not immediately life-threatening; hospitalization or prolongation of hospitalization indicated; disabling; limiting self-care ADL
- Grade 4: Life-threatening consequences; urgent intervention indicated
- Grade 5: Death related to AE

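### DLTs and treatment-related events are counted under conflicting attribution rules, and no separate attribution to radiotherapy, temozolomide or the combination is specified

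*Combined protocol and SAP*

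**What the plan says.** **DLT, wide form.** Section 6 (Safety Lead-ins), which also sets the 2-of-6 and 5-of-15 thresholds, says: "DLT include any severe or life-threatening treatment-related adverse effects that preclude further administration of the study treatments, such as radiation, temozolomide", and then adds continuation of TTFields. The opening sentence of Section 7a (Dose Limiting Toxicity) likewise refers to toxicity that precludes any of the three treatments.

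**DLT, narrow form.** The next paragraph of Section 7a requires that the investigator consider the event "attributable to TTFields or the combination of TTFields with radiation and/or temozolomide". One bullet under that requirement nevertheless describes skin changes caused by radiation.

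**The 33% rule.** Section 7a bars continuation if more than 33% of subjects have a DLT, "unless a modification is made to the level of the particular treatment to which that adverse event is definitely attributable".

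**Treatment-related events.** Section 7a introduces TRAEs under toxicity related to TTFields. Section 6 (Treatment Modalities) applies the term treatment-related to the expected effects of RT and of TMZ. Section 8 reports treatment-related events without saying related to which treatment.

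**Recording.** Section 7 (Recording of an Adverse Event) tells the investigator to "assign attribution of the possible association of the event with use of the investigational device". The scale beneath is headed "Related to investigational drug/intervention". Its detailed entries ask whether the event "follows a known response pattern to the study drug or device", and a later line speaks of study treatment. The Unrelated entry places among alternative causes "other factors such as the subject's clinical state, therapeutic interventions, or concomitant drugs administered to the subject".

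**The concern.** All three primary endpoints depend on attribution, and DLT counts decide whether enrolment proceeds past 6 and past 15 patients. RT and TMZ have substantial expected toxicity of their own. Whether an event due to RT or TMZ alone counts therefore affects both the reported rates and the stopping decisions, and the answer changes with the passage applied. Section 7a also needs two judgements, attribution to the combination and attribution to a particular treatment, for which the recording instructions specify no separate entry.

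**Working it through.** The documents give no expected DLT rate, so there is no planned figure to reproduce. The check has two parts: one event read against each passage, then an illustration of the size.

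**1. One event, read in each place.** Take a neutropenia graded 4 during trimodal therapy, with ANC below 500/mm³, judged due to TMZ alone. The TMZ rules in Section 6 provide for discontinuing TMZ at that count.

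| Place | Test applied | Reading |
|---|---|---|
| Section 6, Safety Lead-ins | Severe, treatment-related, precludes a study treatment | DLT |
| Section 7a, opening | Same in substance | DLT |
| Section 7a, attribution clause | Due to TTFields or a combination that includes it | Not a DLT |
| Section 6, TMZ expected effects | Myelosuppression listed as treatment-related | Treatment-related |
| Section 7a, TRAE text | Placed under TTFields toxicity | Not clearly a TRAE |
| Section 8 | Treatment-related, treatment not named | Undetermined |
| Section 7, recording sentence | Association with the device | Unrelated or unlikely |
| Section 7, scale wording | Drug or device; study treatment | Could be related |

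If one other patient among the first six has a TTFields-attributable DLT, the count is 2 of 6 on the first reading (do not move forward) and 1 of 6 on the third (proceed).

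**2. Size at the first look.** Let d be the probability of a DLT due to TTFields or the combination, and q the probability of a DLT-level event due to RT or TMZ alone. Both are assumptions. The two are taken as independent, and every d event is taken to count under both definitions.

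Narrow clause: p = d. Wide form: p = 1 − (1 − d)(1 − q). In both cases P(2 or more of 6) = 1 − (1 − p)^6 − 6p(1 − p)^5.

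With d = 5%:

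- Narrow, p = 0.05: 1 − 0.7351 − 0.2321 = 3.3%.
- Wide, q = 5%, p = 1 − 0.95 × 0.95 = 0.0975: 1 − 0.5404 − 0.3503 = 10.9%.
- Wide, q = 10%, p = 1 − 0.95 × 0.90 = 0.145: 1 − 0.3907 − 0.3975 = 21.2%.
- Wide, q = 15%, p = 1 − 0.95 × 0.85 = 0.1925: 1 − 0.2772 − 0.3965 = 32.6%.

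**3. Both looks.** A trial that passes the first look with x = 0 or 1 DLT stops at 15 if the next nine patients contribute at least 5 − x. The added probability is the sum over x = 0, 1 of C(6,x) p^x (1 − p)^(6−x) × P(Bin(9,p) ≥ 5 − x). For the four cases above this adds 0.000, 0.003, 0.014 and 0.035. The chance of stopping at either look is then:

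| d | Narrow | Wide, q = 5% | Wide, q = 10% | Wide, q = 15% |
|---|---|---|---|---|
| 5% | 3.3% | 11.2% | 22.6% | 36.1% |
| 10% | 11.8% | 22.6% | 35.4% | 48.9% |

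**The case against.** The best defence is that the Section 7a list is the operative rule. It is the paragraph that formally defines DLTs, Section 6 elsewhere refers to DLT as the protocol defines it, and the Safety Lead-ins wording can be read as a summary. Section 7a also places TRAEs under TTFields toxicity, while the RT and TMZ uses of treatment-related occur in lists of expected effects and not in endpoint definitions.

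This narrows the problem without removing it. The thresholds sit beside the wide wording, Section 7a opens with the wide wording itself, and its narrow list includes a radiation-caused event. Section 8 does not settle the scope.

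Four stronger readings are tempting, and the documents do not support them.

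- *Causality is recorded only to the device.* The recording sentence names only the device, but the scale refers to drug, intervention and study treatment, and the skin examinations call for attribution without naming its object. The defect is inconsistent wording together with the lack of specified separate entries.
- *The other versions of the endpoints could never be recovered from the data.* The case report form is not in the documents. All Grade 3 and higher events are entered whether or not they are thought device-associated, the DLT call is a direct investigator judgement, and DLTs go to the safety committee in a written report.
- *Toxicities shared by TTFields and RT could hardly ever be called definite, so the 33% rule's exception could rarely be used.* Section 7a does not refer to the five-level scale. The requirement that the event "cannot be reasonably explained by other factors such as" concomitant treatment appears under Probable as well as Definite. The plan also gathers relevant evidence, such as correlation with the ceramic disc or adhesive and TTFields breaks while RT continues.
- *A TRAE range can be built from the EF-14 rates in Section 4.* Those figures (43% mild to moderate, 2% severe) cover skin irritation only, so they are not a device TRAE rate.

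**Conclusion.** The inconsistency is in the current text and needs correcting, because it bears on a stopping decision: one patient with an RT- or TMZ-only event can decide the 2-of-6 rule. At an assumed 5% TTFields or combination DLT risk, the choice of passage moves the first-look stopping probability from 3.3% to between 10.9% and 32.6%, for assumed RT/TMZ-only risks of 5% to 15%. These figures rest on assumed, independent rates and show sensitivity; they do not predict what the trial will observe. No size can be put on the effect on the TRAE rates from the documents. Which attribution rule should define a DLT is a clinical decision for the sponsor, and this point takes no position on it.

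**What to change.** 1. Record causality for each event separately for TTFields, RT, TMZ and the combination, on the existing five-level scale, and make the wording of the recording sentence and the scale agree.
2. Before the first interim analysis, reconcile Section 6 (Safety Lead-ins and the RT and TMZ text), Section 7a, Section 7 (Recording of an Adverse Event) and Section 8 to one DLT attribution rule and one TRAE attribution rule, both chosen by the sponsor. State which levels of the scale count as related; Section 7a's attribution clause gives none.
3. Reconcile the wording of the 33% rule on attribution to a particular treatment with that rule, and say whether it refers to the top level of the scale.
4. In the interim and final tables, report the alternative attribution (any study treatment versus TTFields or its combination) as a second row.

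The cost is three further fields on the adverse event form if the present one is kept for TTFields, matching text edits in the sections named, and one extra table row per endpoint. Attribution to a combination will remain a judgement.

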8. STATISTICAL CONSIDERATIONS

Interim analyses of the first and second safety lead-in cohorts will be performed using data collected from the beginning of the study to eight weeks following trimodal therapy for each patient. Patient characteristics will be summarized using means, standard deviations, medians, interquartile ranges, counts, or percentages, as appropriate. Primary endpoints will be summarized using counts and percentages of patients who experienced a treatment-related adverse event, treatment-related serious adverse event, or DLT for safety and stopping rules.

In the second interim analysis, the percentage of patients with inconclusive MGMT methylation status will also be summarized. Patients with inconclusive MGMT methylation status will be removed from the final study analysis, so we will use this percentage to assess the number of additional patients that need to be recruited to meet our sample size requirement of 30 patients. For example, if 2 out of 15 patients have an inconclusive MGMT methylation status at this stage, we will recruit 4 additional patients to meet the sample size requirement.

Using the intention-to-treat approach, the final analyses will be performed on all patients having received at least one day of use from the study device. Patients with an inconclusive MGMT methylation status will be excluded. Patient characteristics will be summarized using

means, standard deviations, medians, interquartile ranges, counts, or percentages, as appropriate.

Primary endpoints will be summarized using counts and percentages of patients who experienced a treatment-related adverse event, treatment-related serious adverse event, or DLT will be reported overall and by event type following trimodal treatment and 8 weeks thereafter to capture any later appearing toxicities. A subgroup evaluation by MGMT methylation status (methylated vs unmethylated) will also be performed.

Kaplan Meier survival analyses will be used to analyze the following secondary endpoints: 1) progression-free survival at 6 months and 2 years, 2) median time-to-death and overall survival at 2 years and 3) duration of TTF use. Log rank tests may be used in Kaplan Meier analyses to test for differences in survival curves amongst known prognostic factors such as age, duration and compliance of TTF use, KPS, extent of resection, IDH mutation status, and MGMT methylation status. The objective response by modified RANO criteria will be summarized with counts and percentages following trimodal treatment and at 2 years. The rate of TTFields compliance will be reported as the percentage of patients who used TTFields at least 75% of the minimum recommended usage of 18 hours a day on average, as assessed monthly.

The intention-to-treat analyses may be supplemented by per-protocol analyses, if the percentage of patients who did not follow standard of care recommendations as outlined for adjuvant and maintenance therapy following trimodal treatment is high.

Power Calculation

As we are expecting that patients will be more susceptible to skin irritation with concurrent therapy than with successive therapy, we focus on severe skin irritation as our endpoint for this power calculation. We expect 5% of patients will experience severe skin irritation based on a 2% rate in the Stupp et al. 2015 study (EF-14)²⁴ which used TTField therapy following initial chemoradiation treatment. Assuming a sample size of 30 patients of whom 5% experience severe skin irritation, we can say with 95% confidence that the true percentage of patients with severe skin irritation is no lower than 2% and no higher than 21% based on a one-sample binomial proportion. Outside of severe skin toxicity, the rate of any adverse event is not expected to differ significantly from that established by the EF-14 trial.

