Study Hypothesis:	TTFields has been shown to be safe and efficacious in large trials with glioblastoma patients in combination with adjuvant temozolomide but concurrent use together with trimodal therapy has not been examined in clinical trials. Our primary hypothesis is that the TTFields treatment, if initiated concurrently along with radiation and temozolomide therapy, would not significantly alter the safety profile. Secondarily, continuation of early initiated TTF along with adjuvant temozolomide treatment as per the standard of care would increase progression and overall survival. The primary hypothesis is safety and will be tested directly in this trial, but the secondary hypothesis would be assessed only with preliminary observations and need validation in a larger trial that is statistically powered for that investigation.
Sample Size:	30 patients total, 6 included in the first safety lead-in and 15 in the second safety lead-in.
Study Population:	Patients with newly diagnosed histologically confirmed glioblastoma after maximally safe resection, with MGMT methylation status in process, are eligible for enrollment.
Primary Endpoint:	The primary endpoint is safety and tolerability of the combined use of TTFields added to standard chemoradiation and TMZ.
Secondary Endpoints:	Our secondary endpoints will be progression-free and overall survival, imaging response by RANO criteria, and duration and compliance of TTF use.

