- 4. Investigator judgment, safety** – Investigator may discontinue treatment due to concerns of safety. This includes significant neurological decline during treatment or requirement of steroids beyond the daily limit of 8mg of dexamethasone or bioequivalent dose for more than 7 consecutive days.
- 5. Lack of compliance** - The Sponsor or investigator may remove a patient from study therapy for lack of compliance to the study protocol. Patients who are using the TTField treatment less than 75% of the minimum recommended usage of 18 hours a day on average, as assessed monthly (13 hours a day or less), unless per officially instituted dose reduction, may be discontinued at the discretion of the investigator or sponsor.
- 6. Inter-current illness** – Illness that prevents further administration of treatment.

Enrollment Plan

a) Anticipated Start Date

- Dosimetric testing and analysis planned for September, 2019.
- Screening planned to begin November, 2019.

b) Total Expected Duration of the Clinical Trial

Anticipated duration of the trial will be 36 months from start of screening to completing two year long-term follow of the last patient enrolled.

c) Expected Duration of Each Subject's Participation

Up to 24 months from subject screening date to the point of study discontinuation based on specified criteria above or completion of the clinical trial.

e) Estimated Time Needed to Select the Required Number of Subjects (i.e., Enrollment Period)

The anticipated initial enrollment period for the 6 subjects in the lead-in cohort will be 4-8 weeks, with 3 subjects from each of the 2 study sites.

Following the interim analysis of safety for the lead-in cohort, there will be an expansion of enrollment to 15 patients, followed by another safety stop and interim analysis. The final cohort will comprise a total of 30 patients between the 2 participating sites. At least 1/3 of the subjects will be enrolled from each of the 2 study sites to ensure even enrollment (i.e., at least 10 subjects at each site). Anticipated duration for subject enrollment will be 6 to 12 months from start of screening to last subject enrolled in study.

Clinical Trial-Related Procedures

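### Minor: the worked example for the MGMT top-up (2 of 15 inconclusive, recruit 4 more) makes no allowance for inconclusive results among the added patients; the same aim calls for 5

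*Combined protocol and SAP*

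**What the plan says.** Section 8 (Statistical Considerations) sets the exclusion that makes a top-up necessary: "Patients with inconclusive MGMT methylation status will be removed from the final study analysis". The inconclusive share is to be summarized at the second interim analysis, which covers the first 15 patients, and Section 8 adds that "we will use this percentage to assess the number of additional patients that need to be recruited". The target is a sample size requirement of 30. No formula is given. The only guide is one worked case: "For example, if 2 out of 15 patients have an inconclusive MGMT methylation status at this stage, we will recruit 4 additional patients". The sentence closes by saying that this is done in order to reach the required size.

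Because inconclusive patients leave the analysis, the 30 in this paragraph can only mean 30 patients who stay in it. Otherwise no top-up would be needed.

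Elsewhere the planned size is given without mention of a top-up. The synopsis (Section 1, Sample Size) has "30 patients total, 6 included in the first safety lead-in and 15 in the second safety lead-in", and the Enrollment Plan in Section 6 has "The final cohort will comprise a total of 30 patients between the 2 participating sites".

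**The concern.** The extra patients have the same MGMT testing and face the same exclusion as the first 30. If 2 in 15 are expected to be inconclusive, some of the added patients will be too. A top-up equal to the expected loss from the first 30 replaces that loss but not the further loss among the replacements. On average it therefore falls short of the target it is meant to reach.

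What is at stake is small but specific: a stated sample-size figure does not reliably deliver its own target. Since no formula accompanies the example, whoever applies the plan after the second interim analysis would probably copy its logic, and the shortfall from that logic grows with the inconclusive rate.

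**Working it through.** **Inputs, all from Section 8.** Target: 30 patients with a conclusive result. Inconclusive share in the example: p = 2/15 = 13.3%. Stated top-up: 4, hence 34 enrolled. The base enrollment of 30 is also in the synopsis and the Enrollment Plan.

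**Reproducing the plan's figure.** 30 × p = 30 × 2/15 = 4.0 exactly. Counting the 2 already observed plus 15 × 2/15 = 2 projected among the next 15 also gives 4. Neither route includes any loss among the 4 added.

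**Expected number analysed with 4 extra.** 34 × 13/15 = 29.47. Starting from the 13 conclusive patients already seen gives the same: 13 + 19 × 13/15 = 29.47. The expected shortfall is 30 − 29.47 = 0.53 patient.

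**Number needed.** For 30 expected conclusive patients, N(1−p) = 30, so N = 30/(13/15) = 34.6, rounded up to 35. Equivalently, the top-up is 30p/(1−p) = 4/(13/15) = 4.6, rounded up to 5. Then 35 × 13/15 = 30.33.

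**Chance of reaching 30.** With 13 conclusive among the first 15, 17 more are needed from the remaining patients. Taking 13/15 as the true conclusive rate:

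- 4 extra (19 remaining): P(Bin(19, 13/15) ≥ 17) = 0.526.
- 5 extra (20 remaining): P(Bin(20, 13/15) ≥ 17) = 0.727.

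The rate itself is poorly known from 15 patients: the exact 95% interval for 2 of 15 runs from 1.7% to 40.5%.

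**If the example's logic were used at other interim counts.** This is an extrapolation, because the plan works only the second row. A top-up of 30p leaves 30(1+p)(1−p) = 30(1−p²) expected conclusive patients, so the expected shortfall is 30p².

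| Inconclusive of 15 | Top-up 30p | Expected conclusive | 30p/(1−p) | Rounded up |
|---|---|---|---|---|
| 1 | 2 | 29.9 | 2.1 | 3 |
| 2 | 4 | 29.5 | 4.6 | 5 |
| 3 | 6 | 28.8 | 7.5 | 8 |
| 4 | 8 | 27.9 | 10.9 | 11 |
| 5 | 10 | 26.7 | 15.0 | 15 |

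**Effect on precision.** The Power Calculation in Section 8 gives limits of 2% and 21% for severe skin irritation with 30 patients. A Wilson 95% interval for 2 events in 30 is 1.8% to 21.3%, which matches after rounding. For 2 events in 29 it is 1.9% to 22.0%. Losing one patient moves the upper limit by 0.7 percentage points.

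**The case against.** Several points can fairly be made for the plan.

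- **No formula is written.** The text says only that the percentage will be used, and then gives an example. That the rule is 30 × p is an inference from one case, although 4 fits it exactly. This stands: the table rows other than 2 of 15 show what would follow from copying the example, not errors in the document.
- **The example does not clearly fail.** A reader might infer that 34 patients will miss 30. That is true only of the mean, and by about half a patient. Given 13 conclusive of the first 15, the most likely and the median number of further conclusive patients among 19 is 17, which makes 30 in total. This stands as a limit on the size of the point. A chance of about 53% is nevertheless weak support for a number presented as meeting the requirement.
- **Little depends on 29 versus 30.** The primary endpoints are summarized as counts and percentages, Section 6 says the secondary endpoints are not powered, and the stopping rules use the first 6 and first 15 patients. In addition, Evaluation of Safety in Section 7 analyses everyone with at least one day of TTFields and mentions no MGMT exclusion. On that definition the safety denominator would not shrink. This too stands; which population applies is a separate question.
- **A contradictory ceiling.** A reader might infer that the synopsis and the Enrollment Plan cap the trial at 30 and so conflict with Section 8. They do not say maximum. They give a planned size, which Section 8 extends on a stated condition. A cross-reference is missing, but there is no demonstrated contradiction.
- **A once-only adjustment.** A reader might also infer that the top-up is fixed at the second interim analysis. Section 8 says when the percentage is summarized and does not bar a later adjustment. Screening in Section 6 and note R of Appendix 3 have pending MGMT results reviewed at each visit until available, so the count can be tracked.

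**Conclusion.** Wrong as written, and minor. The example's 4 should be 5 if the aim is for at least 30 conclusive patients to be expected at the example's rate. With 4, the expectation is 29.5 and the chance of at least 30 about 53%; with 5, they are 30.3 and about 73%. Nothing elsewhere in the documents repairs the figure.

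The conclusion assumes that the added patients are inconclusive at the interim rate, that 2/15 is the true rate, and that the exclusion in Section 8 stays. The likelihood of reaching 30 also assumes that patients' results are independent.

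The documents do not support a claim that the trial's precision suffers in the example, or that enrollment is capped at 30. A larger effect depends on a higher inconclusive rate: the expected shortfall would be about 2 patients at 4 of 15 and about 3 at 5 of 15, and only if the example's logic were carried over.

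**What to change.** In Section 8, change the example to 5 additional patients and state the rule: additional patients = 30p/(1−p), rounded up, where p is the inconclusive share at the second interim analysis. Alternatively, state that recruitment continues until 30 patients have a conclusive MGMT result; this does not rely on a rate estimated from 15 patients, but the final total is then not known in advance. If 4 is kept, state that 29 to 30 conclusive patients are expected.

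For consistency, add a reference to the Section 8 top-up to the Sample Size entry of the synopsis and to the Enrollment Plan in Section 6. This is a clarification, not the correction of a separate error.

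The cost is one sentence in Section 8 and two cross-references. In the example it means one more patient, or none if the expected number is simply restated. At higher rates the formula asks for more than the example's logic would: 11 rather than 8 at 4 of 15, and 15 rather than 10 at 5 of 15.
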